5.5 CONCOMITANT THERAPY

5.5.1 Permitted Concomitant Therapy

Antiemetics are permitted if clinically indicated. Standard supportive care medications are permitted. Use of neutrophil growth factors (filgrastim and pegfilgrastim) or red blood cell growth factors (erythropoietin) is permitted per the American Society of Clinical Oncology (ASCO) guidelines¹⁶. Transfusions may be given in accordance with institutional policy.

Short courses (≤14 days) of steroid treatment for non-cancer related medical reasons (e.g., joint inflammation, asthma exacerbation, rash, antiemetic use and infusion reactions) at doses that do not exceed 100 mg per day of prednisone or equivalent are permitted.

Treatment for autoimmune cytopenias is permitted for <14 days at doses that do not exceed 100 mg per day of prednisone or equivalent.

5.5.2 Prohibited Concomitant Therapy

Any non-study protocol related chemotherapy, anticancer immunotherapy, experimental therapy, or radiotherapy are prohibited during the Treatment Phase. Localized, hormonal, or bone sparing treatment for non-B-cell malignancies may be considered with approval of the medical monitor.

Localized radiotherapy for medical conditions other than the underlying B-cell malignancies are allowed after consultation and approval by the medical monitor.

5.6 MEDICATIONS TO BE USED WITH CAUTION

5.6.1 CYP3A Inhibiting/Inducing Agents

PCI-32765 is metabolized primarily by CYP3A. Avoid co-administration with strong or moderate CYP3A inhibitors and consider alternative agents with less CYP3A inhibition. Coadministration of ketoconazole, a strong CYP3A inhibitor, in 18 healthy subjects increased dose normalized exposure, C_{max} and AUC_{0-last}, of PCI-32765 by 29- and 24-fold, respectively. The maximal observed PCI-32765 exposure (AUC) was ≤2-fold in 37 patients treated with mild and/or moderate CYP3A inhibitors when compared with the highest PCI-32765 exposure in 76 patients not treated concomitantly with CYP3A inhibitors. Clinical safety data in 66 patients treated with moderate (n=47) or strong CYP3A inhibitors (n=19) did not reveal meaningful increases in toxicities. Strong inhibitors of CYP3A (e.g., ketoconazole, indinavir, nelfinavir, ritonavir, saquinavir, clarithromycin, telithromycin, itraconazole, and nefazadone) should be avoided. If a strong CYP3A inhibitor must be used, reduce the PCI-32765 dose to 140 mg or withhold treatment temporarily. Subjects should be monitored for signs of PCI-32765 toxicity. If a moderate CYP3A inhibitor must be used, reduce PCI-32765 to 140 mg for the duration of the inhibitor use. No dose adjustment is required in combination with mild inhibitors. Avoid grapefruit and Seville oranges during PCI-32765 treatment, as these contain moderate inhibitors of CYP3A (see Section 5.3).

Co-administration of PCI-32765 with a strong CYP3A inducer, rifampin, in healthy subjects decreases PCI-32765 plasma concentrations by approximately 10-fold. Avoid concomitant use of strong CYP3A inducers (e.g., carbamazepine, rifampin, phenytoin, and St. John's Wort). Consider alternative agents with less CYP3A induction.

A list of common CYP3A inhibitors and inducers is provided in Appendix 2; a comprehensive list of inhibitors, inducers, and substrates may be found at http://medicine.iupui.edu/clinpharm/ddis/table.aspx. This website is continually revised and should be checked frequently for updates.

5.6.2 Drugs That May Have Their Plasma Concentrations Altered by PCI-32765

In vitro studies indicated that PCI-32765 is not a substrate of P-glycoprotein (P-gp), but is a mild inhibitor (with an IC₅₀ of 2.15 μ g/mL). PCI-32765 is not expected to have systemic drug-drug interactions with P-gp substrates. However, it cannot be excluded that PCI-32765 could inhibit

intestinal P-gp after a therapeutic dose. There are no clinical data available. Therefore, to avoid a potential interaction in the GI tract, narrow therapeutic range P-gp substrates such as digoxin should be taken at least 6 hours before or after PCI-32765.

5.6.3 Concomitant Use of QT Prolonging Agents

Any medications known to cause QT prolongation should be used with caution; periodic electrocardiogram (ECG) and electrolyte monitoring should be considered.

5.6.4 Concomitant Use of Antiplatelet Agents and Anticoagulants

Warfarin or vitamin K antagonists should not be administered concomitantly with PCI-32765. Supplements such as fish oil and vitamin E preparations should be avoided. Use PCI-32765 with caution in subjects requiring other anticoagulants or medications that inhibit platelet function. Subjects with congenital bleeding diathesis have not been studied. For guidance on PCI-32765 and the use of anticoagulants during procedures/surgeries see Section 5.6.5.

Subjects requiring the initiation of therapeutic anticoagulation therapy (e.g., atrial fibrillation), consider the risks and benefits of continuing PCI-32765 treatment. If therapeutic anticoagulation is clinically indicated, treatment with PCI-32765 should be held and not be restarted until the subject is clinically stable and has no signs of bleeding. No dose reduction is required when study drug is restarted.

5.6.5 Guidelines for PCI-32765 Management with Surgeries or Procedures

PCI-32765 may increase risk of bleeding with invasive procedures or surgery. The following guidance should be applied to the use of PCI-32765 in the peri-operative period for subjects who require surgical intervention or an invasive procedure while receiving PCI-32765.

5.6.5.1 Minor Procedures

For minor procedures (such as a central line placement, needle biopsy, thoracentesis, or paracentesis) PCI-32765 should be held for at least 3 days prior to the procedure and should not be restarted for at least 3 days after the procedure. For bone marrow biopsies that are performed while the subject is on PCI-32765, it is not necessary to hold PCI-32765 for these procedures.

5.6.5.2 Major Procedures

For any surgery or invasive procedure requiring sutures or staples for closure, PCI-32765 should be held at least 7 days prior to the intervention and should be held at least 7 days after the

procedure and restarted at the discretion of the investigator when the surgical site is reasonably healed without serosanguineous drainage or the need for drainage tubes.

5.6.5.3 Emergency Procedures

For emergency procedures (unscheduled/urgent), PCI-32765 should be held for a minimum of 7 days after the urgent surgical procedure and until the surgical site is reasonably healed.

5.6.6 Reproductive Toxicity

Reproductive toxicity studies have not been done with PCI-32765. Therefore, women of child-bearing potential who are sexually active must use highly effective contraception during the study and for 90 days after the last dose of PCI-32765. Men who are sexually active, must use highly effective contraception during the study and for 90 days (3 months) after the last dose of PCI-32765. Subjects should promptly notify the investigator if they, or their partner, become pregnant during this period. If a female subject becomes pregnant during the treatment period, she must discontinue PCI-32765 immediately. Pregnancy in a female subject or a male subject's partner must be reported in the same manner as a SAE (refer to Section 7.2.3).

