1.3.2 Toxicology

In safety pharmacology assessments, no treatment-related effects were observed in the central nervous system or respiratory system in rats at any dose tested. Further, no treatment-related corrected QT interval (QTc) prolongation effect was observed at any tested dose in a cardiovascular study using telemetry-monitored dogs.

Based on data from rat and dog including general toxicity studies up to 13 weeks duration, the greatest potential for human toxicity with PCI-32765 is predicted to be in lymphoid tissues (lymphoid depletion) and the gastrointestinal tract (soft feces/diarrhea with or without inflammation). Additional toxicity findings seen in only one species with no observed human correlate in clinical studies to date include pancreatic acinar cell atrophy (rat), minimally decreased trabecular and cortical bone (rat) and corneal dystrophy (dog).

In vitro and in vivo genetic toxicity studies showed that PCI-32765 is not genotoxic. In a rat embryo-fetal toxicity study PCI-32765 administration was associated with fetal loss and malformations (teratogenicity) at PCI-32765 doses that result in approximately 6 times and 14 times the exposure (AUC) in patients administered the dose of 560 mg daily, respectively.

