4.1 INCLUSION CRITERIA

Eligible subjects will be considered for inclusion in this study if they meet all of the following criteria:

 Men and women with recurrent surface immunoglobulin positive B cell non-Hodgkin's lymphoma (NHL) according to WHO classification (including, but not limited to, CLL/SLL, Waldenström's macroglobulinemia [WM], mantle cell lymphoma [MCL], and diffuse large B cell lymphoma [DLBCL]) who have met requirements for roll over from their parent protocol and want to continue study drug.

- 2. Female subjects of childbearing potential must have a negative serum or urine pregnancy test within 3 days of the first dose of study drug and agree to use dual methods of contraception during the study and for 90 days following the last dose with study drug. Post menopausal females (>45 years old and without menses for >1 year) and surgically sterilized females are exempt from this criterion.
- 3. Male subjects must use an effective barrier method of contraception during the study and for 3 months following the last dose if sexually active with a female of childbearing potential.
- 4. Willing and able to participate in all required evaluations and procedures in this study protocol including swallowing capsules without difficulty.
- Ability to understand the purpose and risks of the study and provide signed and dated informed consent and authorization to use protected health information (in accordance with national and local patient privacy regulations).

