7.2.5 Pregnancy

Before study enrollment, subjects must agree to take appropriate measures to avoid pregnancy. However, should a pregnancy occur, consent to provide follow-up information regarding the outcome of the pregnancy and the health of the infant until 30 days old will be requested.

A female subject must immediately inform the investigator if the subject becomes pregnant from the time of consent to 30 days after the last dose of study drug. A male subject must immediately inform the investigator if the subject's partner becomes pregnant from the time of consent to 3 months after the last dose of study drug. Any female subjects receiving PCI-32765 who become pregnant must immediately discontinue study drug. The investigator should counsel the subject, discussing any risks of continuing the pregnancy and any possible effects on the fetus.

Although pregnancy itself is not regarded as an AE, the outcome will need to be documented. Any pregnancy occurring in a subject or subject's partner from the time of consent to 30 days after the last dose of study drug must be reported. Record any occurrence of pregnancy on the Pregnancy Report Form Part I and fax to Pharmacyclics Drug Safety, or designee, within 24 hours of learning of the event. The pregnant female will be followed for outcome, which is defined as elective termination of the pregnancy, miscarriage, or delivery of the fetus. For pregnancies with an outcome of live birth, the newborn infant will be followed until 30 days old by completing the Pregnancy Report Form Part II. Any congenital anomaly/birth defect noted in the infant must be reported as a SAE.

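### Section 5.6.6 says no reproductive toxicity studies exist although Section 1.3.2 reports one with malformations, and its undefined contraception standard does not match inclusion criteria 2 and 3

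*Protocol*

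**What the plan says.** **On the evidence.** Section 5.6.6 (Reproductive Toxicity) begins: "Reproductive toxicity studies have not been done with PCI-32765". The next sentence starts with *Therefore* and sets the contraception rule. Section 1.3.2 (Toxicology) states: "In a rat embryo-fetal toxicity study PCI-32765 administration was associated with fetal loss and malformations (teratogenicity", at doses giving "approximately 6 times and 14 times the exposure (AUC) in patients administered the dose of 560 mg daily", respectively. Section 1.3.2.1 adds that animal fertility studies have not been conducted.

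**On women.** Inclusion criterion 2 (Section 4.1, repeated in the synopsis) asks females of childbearing potential to "agree to use dual methods of contraception during the study and for 90 days following the last dose with study drug". It exempts only postmenopausal and surgically sterilized women. Section 5.6.6 says that "women of child-bearing potential who are sexually active must use highly effective contraception during the study and for 90 days after the last dose".

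**On men.** Criterion 3 says: "Male subjects must use an effective barrier method of contraception during the study and for 3 months following the last dose if sexually active", and limits this to men whose partner is a female of childbearing potential. Section 5.6.6 says: "Men who are sexually active, must use highly effective contraception during the study and for 90 days (3 months) after the last dose".

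Section 5.6.6 refers the reader only to Section 7.2.3, for reporting a pregnancy. It does not refer to Section 4.1, and Section 4.1 does not refer to it. The protocol does not define *highly effective*.

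**The concern.** There are two problems, and the first is the more serious.

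First, the section to which a site turns for reproductive risk presents a known teratogenic finding as an absence of data. Someone who reads 5.6.6 alone would not know that the animal study was done and was positive.

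Second, a site that follows 5.6.6 in good faith can advise a subject in a way that does not satisfy the inclusion criteria, and the reverse is also possible. Contraception carries much of the protection here. Appendix 3 schedules pregnancy tests only at Screening and at the Safety Follow-up Visit, while treatment may continue for as long as there is no progression or unacceptable toxicity.

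**Working it through.** No sample size, event count or error rate is involved, so there is no plan figure to reproduce. The check is a comparison of current protocol texts.

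**Step 1: the premise of 5.6.6.**
- 5.6.6: no reproductive toxicity studies done.
- 1.3.2: a rat embryo-fetal toxicity study was done and was positive, at about 6 times (fetal loss) and 14 times (malformations) the AUC at 560 mg daily. These multiples are taken as the protocol states them.
- 1.3.2.1: fertility studies, specifically, not conducted.

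The first two statements cannot both be true. Reading the 5.6.6 sentence as meaning fertility studies only does not rescue it. The section is about avoiding and reporting pregnancy, so an embryo-fetal study is the evidence that bears on it most directly.

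**Step 2: the rules side by side.**

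| | Criteria 2 and 3 (4.1, synopsis) | Section 5.6.6 |
|---|---|---|
| Women: who | All of childbearing potential | Those of childbearing potential who are sexually active |
| Women: method | Dual methods | Highly effective, number of methods not stated |
| Men: who | Sexually active with a female of childbearing potential | All sexually active men |
| Men: method | Effective barrier | Highly effective |
| Period | Study plus 90 days (women) or 3 months (men) | Study plus 90 days, equated with 3 months for men |

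The period agrees. Method and population differ for each sex.

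**Step 3: can a subject meet one rule and not the other?**
- Sexually active woman of childbearing potential on a single highly effective method: meets 5.6.6, not criterion 2.
- The same woman on two methods, at least one of them highly effective: meets both.
- Man with a partner of childbearing potential who uses only a barrier: meets criterion 3. Whether he meets 5.6.6 cannot be decided, because the term is undefined.
- The same man relying on a highly effective method that is not a barrier: meets 5.6.6, not criterion 3.
- Woman who is not sexually active, or man whose partner cannot conceive: covered by one rule and not the other, but with little bearing on fetal exposure.

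The differences that matter are therefore in method: chiefly the male method, and then the woman on a single highly effective method.

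**The case against.** The strongest reply is that the rules are cumulative. Criterion 2 binds every enrolled woman of childbearing potential for the whole period, and nothing in 5.6.6 releases her from dual methods. That stands. It settles which rule governs women, but it leaves the male method open, leaves *highly effective* undefined, and does not tell a reader of 5.6.6 that a stricter rule exists elsewhere.

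A second reply is that the false sentence loosens no instruction. Contraception is mandatory either way, a pregnant subject must stop the drug at once, and the teratogenicity finding appears in the same protocol, which also sends readers to the Investigator's Brochure. This is right about consequence and keeps the point modest. It does not make the sentence true.

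A third reply concerns Section 7.2.5: "Before study enrollment, subjects must agree to take appropriate measures to avoid pregnancy". A reader might infer a third, vaguer contraception rule. The text does not support that. The sentence introduces the pregnancy-reporting procedure and is naturally read as recalling what subjects agree to at entry.

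**Conclusion.** The point holds as a correction of text. Section 5.6.6 makes a statement that Section 1.3.2 contradicts, and its contraception standard is undefined and not aligned with criteria 2 and 3. That subjects might be advised differently is a possibility created by the wording; nothing in the documents shows that it has happened. The documents give no number of women of childbearing potential or of sexually active men, so the number affected cannot be stated. Anyone who meets both rules is unaffected. No endpoint, analysis or statistical quantity is touched.

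Three stronger readings are not supported:
- A reader might infer that 5.6.6 relaxes the dual-method rule for women. It does not.
- A reader might infer that the rat finding is the real reason for the contraception rule. The protocol does not say so. The only rationale it gives is the incorrect one in 5.6.6.
- A reader might scale the rat exposure multiples to the 840 mg maximum to express the seriousness of the problem. Section 1.3.3 says only that exposure rose with dose, so the scaling would need an assumption, and the result would not measure a wording conflict.

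**What to change.** 1. Replace the first sentence of 5.6.6 with the embryo-fetal findings and exposure multiples from 1.3.2, and add the statement from 1.3.2.1 that fertility studies have not been conducted.
2. Make 5.6.6 refer to criteria 2 and 3 in Section 4.1 as the single contraception rule, and keep the populations of Section 4.1.
3. Keep dual methods for women of childbearing potential.
4. Define *highly effective* once, without extending that standard to women who are not sexually active.
5. Agree one male method and state it in identical words in the synopsis, 4.1 and 5.6.6.

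The cost is an amendment of wording in those places, with no added visit, test or analysis. Keeping the 4.1 populations means that 5.6.6 would no longer cover men whose partners are not of childbearing potential, which has little bearing on fetal exposure. No duty is added for those men, nor for women who are not sexually active. The consent form is not available here, so no fault in it is alleged. If it repeats either text, it should be brought into line at the same time.

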5.6.7 Overdose Instructions

Any dose of study drug in excess of that specified in this protocol is considered to be an overdose. Signs and symptoms of an overdose that meet any SAE criterion must be reported as an SAE in the appropriate time frame and documented as clinical sequelae to an overdose. There is no specific antidote for ibrutinib. In the event of an overdose, subjects should be closely monitored and given appropriate supportive treatment.

6.0 STUDY PROCEDURES

The Schedule of Assessments is shown in Appendix 3. Descriptions of the scheduled evaluations are outlined below and complete information on study drug and dosing is provided in Section 5.0.

Before study entry, throughout the study, and at the follow-up evaluation, various clinical and diagnostic laboratory evaluations are outlined. The purpose of obtaining these detailed measurements is to ensure adequate safety and tolerability assessments. Clinical evaluations and laboratory studies may be repeated more frequently if clinically indicated. All results from these evaluations must be captured in the provided electronic case report forms (eCRFs).

6.1 DESCRIPTION OF PROCEDURES

Informed Consent

Screening

The subject must read, understand and sign the IRB-approved informed consent form (ICF) confirming his or her willingness to participate in this study before initiating any screening activity that is not standard of care. Subjects must also grant permission to use protected health information.

Medical History

Screening

Medical history, concomitant medications, and any ongoing signs or symptoms from the prior PCI-32765 protocol must be recorded in the site's source documentation.

Adverse Events

At all visits (except Post-treatment and Post-PD follow up assessments)

The accepted regulatory definition for an AE is provided in Section 7.1. Adverse events that meet the criteria for SAEs, events of special interest (Section 7.2.4), and AEs of grade 3 or higher in severity will be recorded from the subject's first dose of study drug until 30 days after study drug discontinuation or start of a new anticancer therapy. Important additional requirements for reporting SAEs are explained in Section 7.2.

Concomitant Medication Use

At screening visit and during study when associated with protocol specified AE or SAE. Verify concomitant medication use to ensure subjects' eligibility to remain on study and when associated with a protocol specified AE/SAE. See Section 7.0 for further AE/SAE details.

Confirmation of Eligibility

Screening

Perform all necessary procedures and evaluations to document that the subject meets each eligibility criterion. Screening evaluations must be completed within 14 days before the subject's first dose of PCI-32765 under this protocol.

Physical Examination and Vital Signs

At all visits (except Post treatment and Post PD follow up assessments)

The screening physical examination will include, at a minimum, the general appearance of the subject, height (screening only) and weight, and examination of the skin, eyes, ears, nose, throat, lungs, heart, abdomen, extremities, musculoskeletal system, nervous system, and lymphatic system.

Symptom-directed physical exams will be done during the treatment period and at the Safety Follow-up Visit.

Vital signs will include blood pressure, pulse, respiratory rate, and body temperature. Vital signs and weight will be measured at every visit. Screening vital signs and weight do not need to be repeated if performed on prior PCI-32765 protocol within 14 days before the first administration of study drug on this protocol.

Eye-related Symptom Assessment

At Screening and all physical exams while on Treatment and Safety Follow-up.

The subjects will be asked about eye-related symptoms at Screening and with all subsequent physical exams while on treatment.

If there are any eye-related symptoms of severity Grade ≥ 2 at Screening or if the subject develops any eye-related symptoms of severity Grade ≥ 2 while on study treatment, an ophthalmologic evaluation/consult must be performed and the outcome must be reported on the ophthalmologic eCRF.

ECOG Performance Status

Treatment Phase and Safety Follow-up Visit

The ECOG performance index is provided in Appendix 1.

Hematology

Screening, Treatment Phase and Safety Follow-up Visit

Hematology must include complete blood count with differential and platelet counts. Testing will be performed at the study center's local laboratory or other clinical laboratory listed on the investigator's form FDA 1572. Screening hematology does not need to be repeated if performed on prior PCI-32765 protocol within 14 days before the first administration of study drug on this protocol. Subjects who roll into PCYC-1103-CA Study with < 12 months of study drug exposure will need to have hematology performed every 30 days (±7 days) until completion of 12 months on study drug and then hematology will be extended to every 3 months (±7 days).

Serum Chemistry

Screening, Treatment Phase and Safety Follow-up Visit

Serum chemistry must include glucose, calcium, albumin, total protein, sodium, potassium, CO₂, chloride, blood urea nitrogen (BUN), creatinine, alkaline phosphatase, ALT, AST, and total bilirubin. Testing will be performed at the study center's local laboratory or other clinical laboratory listed on the investigator's form FDA 1572. Screening chemistry does not need to be repeated if performed on prior PCI-32765 protocol within 14 days before the first administration of study drug on this protocol.

Urine Pregnancy Test

Screening and Safety Follow-up Visit

Pregnancy tests are required only for women with childbearing potential. Testing will be performed at the study center's local laboratory or other clinical laboratory listed on the investigator's form FDA 1572.

ECG

Treatment Phase and Safety Follow-up Visit

ECGs should be performed at the investigator's discretion, particularly in subjects with arrhythmic symptoms (e.g., palpitations, lightheadedness) or new onset dyspnea.

Subjects should be in supine position and resting for at least 10 minutes before study-related ECGs. During visits in which both ECGs and blood draws are performed, ECGs should be performed first.

Pharmacodynamics and Pharmacokinetics

Only when subject progresses

At a visit when it is determined that a subject has progressed, collect blood samples for pharmacodynamic and pharmacokinetics analyses (e.g., Btk occupancy and B cell activation).

- Pharmacodynamic sample should be collected 4 hours post last dose of PCI-32765.
- Pharmacokinetic samples should be collected pre-dose and 4 hours post last dose of PCI-32765.

If Pharmacodynamic and Pharmacokinetic samples cannot be collected at specified timepoints, draw a random sample and capture time of collection and time of last PCI-32765 dose.

Refer to the laboratory binder for instructions on collecting and processing these samples.

If available, tumor samples should also be collected at the visit when disease progression is determined.

Predictive Biomarkers and Mechanisms of Treatment Resistance

Treatment Phase

Blood samples will be collected and assessed or maintained centrally to evaluate potential biomarkers related to response to therapy and/or to investigate potential mechanisms of treatment resistance. These samples may be later characterized by technologies such as gene expression profiling, mutational analysis by sequencing, or proteomic assays. Inhibition of BTK and other related kinases may also be explored in these cells. It is expected that these efforts may identify genes and pathways associated with primary or later development of resistance to PCI-32765 by comparison of subjects with variable outcomes which could potentially generate biomarkers that could assist with future development of this compound.

Disease Assessment

Treatment Phase and Post-treatment Follow-up Phase

Disease assessments, as outlined by histology-specific guidelines, should be performed every 3 cycles (±7 days) while on study treatment. Disease assessments will include physical examination, disease-related symptoms, CBC, radiologic exam by computed tomography (CT) scan or positron emission tomography (PET), and/or bone marrow biopsy (refer to Section 6.2 for response assessment guidelines). Data from bone marrow examinations, including analysis for minimal residual disease (MRD) (bone marrow or peripheral blood if bone marrow is unavailable or considered inappropriate), will be collected and should be performed if subject meets all other criteria for CR.

Study Drug Accountability

At all visits (except Follow-up Phase)

Refer to Section 9.8.

